#### 6.3.6.2 Duration of Response

The duration of response (DOR) is measured from the time measurement criteria are met for CR or PR (whichever is first recorded) until the first date that recurrent or progressive disease is objectively documented (taking as reference for progressive disease the smallest measurements recorded since the treatment started), death, or, in the absence of PD, date of last assessment.

#### 6.3.6.3 Progression-Free Survival

Progression-free survival (PFS) is defined as the duration of time from the date of study enrollment until time of disease relapse, disease progression, or death, whichever occurs first.

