#### 1.1.2 Secondary Objectives

- To determine the best overall response rate (CR + PR) of triplet combination therapy with magrolimab, obinutuzumab, and venetoclax
- To determine the rate of complete molecular remission (MRD negativity) by flow cytometry or similar assays as they become available in patients after triplet combination therapy with magrolimab, obinutuzumab, and venetoclax (in CLL patients only)
- To determine the duration of response (DOR) of triplet combination therapy with magrolimab, obinutuzumab, and venetoclax
- To estimate progression-free survival (PFS), event-free survival (EFS), and overall survival (OS) of triplet combination therapy with magrolimab, obinutuzumab, and venetoclax

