#### **2.3.2.2 Arms**

| Number | Name   | Description  |
|---------------|---|---|
| 1             | Experimental treatment:
FL Dose-finding                | Magrolimab IV with a 1 mg/kg priming dose followed by 30mg/kg loading and maintenance doses + obinutuzumab IV 1000mg + venetoclax 800mg PO combination administered to 6 patients for six (6) cycles (28-days each, Cycles 1-6); further treatment with additional cycles will be response-adapted. Note: DLT assessment of the magrolimab + obinutuzumab + venetoclax triplet will take place during Cycle 1. If $\geq 2$ patients experience DLT, an additional 6 patients will be enrolled at DL(-1) of venetoclax 600mg with magrolimab and obinutuzumab.   |
| 2             | Experimental treatment:
MZL, MCL, and CLL Dose-finding | Magrolimab IV with a 1 mg/kg priming dose followed by 30mg/kg loading and maintenance doses + obinutuzumab IV 1000mg + venetoclax ramp-up to target dose of 400mg over 5 weeks (35 days, Cycle 1) administered to 6 patients. Triplet combination of magrolimab + obinutuzumab + venetoclax (target dose, no ramp-up) will continue for five (5) additional cycles (28-days each, Cycles 2-6); further treatment with additional cycles will be response-adapted. Note: DLT assessment of the magrolimab + obinutuzumab + venetoclax triplet will take place during Cycle 1. If $\geq 2$ patients experience DLT, an additional 6 patients will be enrolled at DL(-1) of venetoclax 200mg with magrolimab and obinutuzumab. |

| Number | Name  | Description  |
|--------|---|--|
| 3      | Experimental treatment:
FL Dose expansion            | Window of magrolimab IV with a 1 mg/kg priming dose followed by 30mg/kg loading and maintenance doses + obinutuzumab IV 1000mg combination for two (2) cycles (28-days each, Cycles -2 and -1), then venetoclax will be added at target dose (dose determined from Arm 1). Triplet combination treatment with magrolimab + obinutuzumab + venetoclax will be 6 cycles (28-days each, Cycles 1-6); further treatment will be response-adapted.  |

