#### **3.10.1 Criteria for Removal from Protocol Therapy**

- Disease progression
  - A patient may be granted an exception to continue on study treatment with initial radiographic progression if they meet the criteria outlined in Section [3.6](#)
  - Patient who progresses prior to initiation of venetoclax will not be removed from the protocol, but will move on immediately to the triplet therapy or safety ramp-up phase
- Completion of protocol therapy
- Intercurrent illness that prevents further administration of treatment
- Requirement for use of prohibited therapies as listed in Section [4.2](#)
- Pregnancy
- Patient requests to be withdrawn from protocol therapy
- Noncompliance with trial treatment or procedure requirements in the opinion of the investigator; such a decision/rationale will be clearly noted in the medical record
- Investigator's decision to withdraw the patient if felt to be in the best interest of the patient; such a decision/rationale will be clearly noted in the medical record

- Unacceptable adverse event(s) (see Section 3.3), unless it is felt by the Principal Investigator to be in the patient's best interests to remain on study in exceptional circumstances (e.g., discontinue offending study agents while continuing others).

All subjects, regardless of reason for discontinuation of study treatment (with the exception of withdrawal of consent; unless consent to follow-up activities is documented) will be followed for progression and survival.

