#### 6.3.6.4 Event-Free Survival

Event-free survival (EFS) is defined as the duration of time from the date of study enrollment until time of disease relapse, disease progression, alternative anti-lymphoma therapy including radiation, or death, whichever occurs first.

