Based on these estimates, up to 24 patients may be required for venetoclax dose-finding. These, in addition to 42 total treated patients required to complete the dose expansion phase brings the total number of patients required to complete the study to 66. To allow for a small number of inevaluable patients and screen failures, the accrual ceiling will be set at 76 patients. It is expected that 3 to 4 years may be required to complete accrual, including dose-finding and expansion cohorts. Patients enrolled in dose-finding cohorts who are treated at the same dose-level as the expansion cohorts may be analyzed together with the dose-expansion cohorts at the end of the study (Cohort 1 with Cohort 3, and Cohort 2 with Cohorts 4, 5 and 6, respectively).

As mentioned earlier in Section [1.2.6.2.1.2](#), recent reports indicate that MZL patients may be at a higher risk of infection-related AEs with fatal outcome when obinutuzumab was used in combination with chemotherapy. As an early stopping rule, if  $\geq 2$  subjects have infection-related SAEs or any subject experiences a fatal infection-related AEs from the first 6 subjects on study, we will hold further enrollment, and a comprehensive safety analysis will be performed.

In addition, an early stopping rule will be implemented for all histologies, if a substantial number of patients have to discontinue therapy due to unacceptable toxicity. If at any point after the first 20 patients are enrolled, 25% or more patients have been unable to complete therapy due to unacceptable toxicity or if at any point 2 or more deaths or grade 4 hemolytic anemia events occur that are probably or definitely related to study therapy, then study enrollment for all histologies will be suspended for a formal assessment of the overall safety profile of the study design. This early stopping rule is applicable throughout the duration of the study.

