| Research Saliva/Buccal (baseline), Blood Samples                         |                        |   |                             |            |  |                        | See Research Sample Calendar in Section 5.1 |              |                                   |   |                                  |                             |
| Survival Status   |                        |   |                             |            |  |                        |   |              |                                   |   |                                  | X                           |

**†Window Portion:** Applies only to patients enrolled in the dose expansion cohorts.

**△**Additional monitoring for TLS during C1 of triplet combination therapy is described in Section 4.1.2.

**NOTE:** Perform any other assessments and/or tests as clinically indicated at the discretion of the investigator.

 Screening and Baseline evaluations should be performed within 28 days prior to enrollment and dosing, respectively, with the following exceptions: Confirmation of diagnosis (no time limit); HIV antibody, Hepatitis B surface antigen and Hepatitis C antibody (within 3 months); Bone marrow assessments (within 12 months). See Section 2.2. **NOTE:** Any screening tests performed within the time frame for baseline do not need to be repeated.

 Within 28 days prior to dosing in Window on Cycle -1 Day 1, unless otherwise noted to be within 14 days (\*) or 7 days (^).

 To be done at treatment discontinuation (+/- 2 weeks) or may coincide with the safety follow-up visit. If treatment is discontinued for a reason other than disease progression, assessments should be repeated at the time of progression. If subject to initiate new anti-cancer therapy assessments should occur before the first dose of the new therapy.

 Follow-up prior to disease progression to occur about every 3 months (+/- 2 weeks) for first 2 years after therapy, every 6 months for years 3-5 (+/- 4 weeks), and then annually (+/- 6 weeks) at the discretion of investigator.

 After disease progression or initiation of new anti-cancer therapy, contact for survival about every 3-6 months (+/- 4 weeks).

 Physical exams to include history, vitals, weight, and height (screening only).

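### PFS and EFS are stated as results of the triplet but timed from enrollment, so in the expansion cohorts they include the doublet window and end at a window progression before any venetoclax is given.

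*Combined protocol and SAP*

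**What the plan says.** - **Objective (1.1.2):** "To estimate progression-free survival (PFS), event-free survival (EFS), and overall survival (OS) of triplet combination therapy".
- **PFS (6.3.6.3):** "from the date of study enrollment until time of disease relapse, disease progression, or death, whichever occurs first".
- **EFS (6.3.6.4):** "from the date of study enrollment until time of disease relapse, disease progression, alternative anti-lymphoma therapy including radiation, or death, whichever occurs first". Neither definition makes an exception for the window.
- **Window (2.3.2.2, Arm 3; Arm 4 is parallel):** the doublet is given as a "combination for two (2) cycles (28-days each, Cycles -2 and -1), then venetoclax will be added at target dose". The study calendar (Appendix G) notes that the window "Applies only to patients enrolled in the dose expansion cohorts". Table 11 starts venetoclax on Day 1 of Cycle 1 in the dose-finding arms.
- **Progression in the window:** section 3.10.1 states, "Patient who progresses prior to initiation of venetoclax will not be removed from the protocol", and sends that patient straight on to the triplet or the ramp-up. Section 3.1.2 permits the same move for patients who are tolerating therapy.
- **Pooling (10.2):** dose-finding patients treated at the same dose level "may be analyzed together with the dose-expansion cohorts at the end of the study", Cohort 1 with 3 and Cohort 2 with 4, 5 and 6.
- **Analysis (10.4.3):** Kaplan-Meier estimation. No time origin at triplet start, no rule for window progression and no separation by window is given. Reporting by cohort and histology is stated for ORR and CR rate, not for PFS or EFS. Section 10.4.7 plans no subgroup analyses.

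**The concern.** The objective and the measurement do not match. In Cohorts 3–6 the clock runs through two cycles of a different regimen before the triplet begins, with two opposite effects:

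- A patient who progresses on the doublet has a PFS and EFS event before receiving venetoclax. The protocol treats that progression as a point to go on to the triplet, but nothing the triplet then does can enter the curve.
- A patient who does not progress in the window carries that time into a figure labelled as triplet PFS.

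A curve combining these patients with Cohorts 1–2 would also put two different time origins, relative to the triplet, on one axis. A reader of the published median could not tell how much of it describes the triplet.

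**Working it through.** **1. Head-count.** The plan states no PFS assumption, power or event count, so only the patient numbers can be reproduced. Dose-finding: 2 × (6 + 6) = 24. Expansion: 18 + 6 + 12 + 6 = 42. Total 66, as section 10.2 states. If each dose-finding cohort stays at its first dose level, the permitted pools would contain 6 of 24 (25%) no-window patients in FL and 6 of 30 (20%) in MZL/MCL/CLL.

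**2. The clocks side by side.**

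| | Cohorts 1–2 | Cohorts 3–6 |
|---|---|---|
| PFS/EFS clock starts | enrollment | enrollment |
| Scheduled doublet-only time | none | 2 × 28 = 56 days |
| First venetoclax | Cycle 1 Day 1, the first treatment day | Cycle 1 Day 1, after the window |
| Progression on study drugs before venetoclax | not possible by schedule | possible; ends PFS/EFS, patient may continue |

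In months, W = 56 / 30.4375 = 1.84.

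**3. Size, as an illustration.** The documents give neither a window-progression rate for this doublet (q) nor an expected triplet PFS (median m). Both are assumed here. Model: exponential PFS from triplet start with median m; a share q progress in the window; all other patients start the triplet at time W. On the enrollment clock, for t ≥ W:

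S(t) = (1 − q) × 2^(−(t − W)/m), so median = W + m × [1 + log2(1 − q)].

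Example, m = 12 and q = 20%: 1.84 + 12 × (1 − 0.322) = 9.98 months.

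Pooled FL (18 with a window, 6 without): median = m × log2{[18(1 − q) × 2^(W/m) + 6] / 12}.

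| q | Expected window progressions of 42 | Expansion median, m = 12 | Pooled FL median, m = 12 | Expansion median, m = 24 |
|---|---|---|---|---|
| 0% | 0 | 13.84 | 13.40 | 25.84 |
| 5% | 2.1 | 12.95 | 12.72 | 24.06 |
| 10% | 4.2 | 12.02 | 12.01 | 22.19 |
| 20% | 8.4 | 9.98 | 10.51 | 18.11 |
| 30% | 12.6 | 7.67 | 8.86 | 13.49 |

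On a clock starting at Cycle 1 Day 1, the median is m in every row.

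**4. Direction.** The two effects cancel at q = 1 − 2^(−W/m): about 10% for m = 12 and 5% for m = 24. Below that, the enrollment clock flatters the triplet; above it, it penalizes the triplet.

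**5. Will the rule be needed?** At q = 10%, the chance of at least one window progression among the 12 MCL patients is 1 − 0.9^12 = 72%.

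**6. Against sampling error.** With m = 12, 12-month PFS is 50.0% on the triplet clock. On the enrollment clock it is 55.6% at q = 0 and 44.5% at q = 20%. The binomial standard error at n = 18 with complete follow-up is √(0.5 × 0.5 / 18) = 11.8 points, so the shift is about half a standard error in either direction.

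**The case against.** **The enrollment clock is legitimate.** Section 10.1.2 ties ORR and molecular remission to the triplet but lists DOR, EFS, PFS and OS without that qualifier. Read with section 6.3.6, these could be meant as times for the whole strategy. This stands to the extent that enrollment-based PFS is not wrong and should be kept. It does not remove the mismatch: section 1.1.2 assigns the result to the triplet, and nothing else says how window progression is to be read.

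**Little depends on it.** PFS and EFS are descriptive, expansion sizes follow expected accrual, and section 10.2 calls the assessment preliminary. This stands, and it limits the weight of the point.

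**Stronger readings that a reader might infer, and why they fail:**

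- *That triplet durability will be badly understated in MCL.* Section 1.2.6.3 gives a median PFS of 2.7 months on obinutuzumab alone. An exponential curve would then put 1 − 2^(−1.84/2.7) = 38% of progressions inside the window. That median comes from 4 patients (range 0.3–36.1 months); 11 patients at the lower dose gave 2.6 months. Neither group received magrolimab. Two reported response durations of about 30 months also fit such a curve poorly. This cannot serve as an estimate of q.
- *That the plan will produce one mixed curve, and that it would be uninterpretable.* Section 10.2 only permits joint analysis and does not name PFS or EFS. In the illustration, the pooled FL median ranges from close to m to several months away from it, depending on q.
- *That aligning clocks makes the cohorts poolable.* Cohorts 3–6 reach Cycle 1 after two antibody cycles expected to reduce bulk (4.1.2.1) and after meeting Table 9, some having already progressed. Cohorts 1–2 start all three drugs together. A common clock does not make these one regimen.

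**Conclusion.** The concern holds as a mismatch between the objective and its measurement. Followed literally, the plan counts doublet-only progressions as failures of the triplet and adds up to 56 scheduled days of doublet time for the other expansion patients. The net bias can be positive or negative.

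Its size is not determinable from the documents. The span of 13.8 to about 10.0 months (0% to 20% window progression) rests on an assumed 12-month median, exponential times, and the same later prognosis whether or not a patient progressed in the window. If window progressors do worse on the triplet, the downward shift is smaller than shown.

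OS shares the time origin, but window progression is not an OS event, so only the added doublet time applies. The dose-limiting-toxicity rules, the primary safety endpoint and the total of 66 are untouched. This should be corrected before analysis, but it does not threaten the trial's main purpose.

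**What to change.** 1. Keep PFS and EFS from enrollment, labelled as results for the whole regimen: window plus triplet in Cohorts 3–6.
2. For the stated objective, add PFS and EFS from triplet Cycle 1 Day 1. Use the last scan before Cycle 1 as the reference, so that window progression is not an event.
3. Report the number who progressed in the window and the number who never started the triplet.
4. Show dose-finding and expansion cohorts separately for PFS and EFS. If they are pooled at all, do so only on the Cycle 1 Day 1 clock and beside the separate curves.

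The cost is a few lines of analysis text and one extra set of curves. Appendix G already schedules CT and PET after the window, so no visit, treatment or sample-size change is needed. The drawback is that the triplet clock is conditional on reaching venetoclax and leaves out those who do not, so both sets of curves must be shown. Fixing the clocks in advance also avoids choosing one after the window progressions are known.

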#### 6.3.6.4 Event-Free Survival

Event-free survival (EFS) is defined as the duration of time from the date of study enrollment until time of disease relapse, disease progression, alternative anti-lymphoma therapy including radiation, or death, whichever occurs first.

#### 6.3.6.5 Overall Survival

Overall survival (OS) is defined as the time from study enrollment until death from any cause.

#### 6.3.6.6 Complete Response Rate

The proportion of patients who achieve a PET-negative complete response (CR) in accordance with the 2014 Lugano classification of the International Working Group Criteria for Non-Hodgkin's Lymphoma([125](#)) or International Workshop Group on CLL (iwCLL) criteria.

#### 6.3.6.7 Complete Molecular Remission Rate

The proportion of patients who achieve both a complete response and are negative on molecular assays for MRD after therapy.

### 6.3.6.8 Objective Tumor Response Rate

The proportion of patients who achieve at least a partial response (PR) to therapy.

## 6.4 TOXICITY CRITERIA

The following adverse event management guidelines are intended to ensure the safety of each patient while on the study. The descriptions and grading scales found in the revised NCI Common Terminology Criteria for Adverse Events (CTCAE) version 5.0 will be utilized for AE reporting. All appropriate treatment areas should have access to a copy of the CTCAE version 5.0. A copy of the CTCAE version 5.0 can be downloaded from the CTEP web site ([http://ctep.cancer.gov/protocolDevelopment/electronic\\_applications/ctc.htm](http://ctep.cancer.gov/protocolDevelopment/electronic_applications/ctc.htm)).

## 7 NIH REPORTING REQUIREMENTS / DATA SAFETY MONITORING PLAN

### 7.1 DEFINITIONS

Please refer to definitions provided in Policy 801: Reporting Research Events found at: <https://irbo.nih.gov/confluence/pages/viewpage.action?pageId=36241835#Policies&Guidance-800Series-ComplianceandResearchEventReportingRequirements>.

### 7.2 OHSRP OFFICE OF COMPLIANCE AND TRAINING/IRB REPORTING

#### 7.2.1 Expedited Reporting

Please refer to the reporting requirements in Policy 801: Reporting Research Events and Policy 802 Non-Compliance Human Subjects Research found at:

<https://irbo.nih.gov/confluence/pages/viewpage.action?pageId=36241835#Policies&Guidance-800Series-ComplianceandResearchEventReportingRequirements>. Note: Only IND Safety Reports that meet the definition of an unanticipated problem will need to be reported per these policies.

#### 7.2.2 IRB Requirements for PI Reporting at Continuing Review

Please refer to the reporting requirements in Policy 801: Reporting Research Events found at: <https://irbo.nih.gov/confluence/pages/viewpage.action?pageId=36241835#Policies&Guidance-800Series-ComplianceandResearchEventReportingRequirements>.

### 7.3 NCI CLINICAL DIRECTOR REPORTING

Problems expeditiously reviewed by the OHSRP in the NIH eIRB system will also be reported to the NCI Clinical Director/designee; therefore, a separate submission for these reports is not necessary.

In addition to those reports, all deaths that occur within 30 days after receiving a research intervention should be reported via email unless they are due to progressive disease.

To report these deaths, please send an email describing the circumstances of the death to [[contact]](mailto:[contact]) within one business day of learning of the death.

## 7.4 NIH REQUIRED DATA AND SAFETY MONITORING PLAN

### 7.4.1 Principal Investigator/Research Team

The clinical research team will meet on a regular basis (approximately weekly) when patients are being actively treated on the trial to discuss each patient. The clinical research team will prepare a

monthly report on the occurrence of any grade 3 or 4 hemolytic anemia events. This report will be provided to Sponsor (OSRO) who will share the information with Gilead and Genentech. In the event of a grade 3 or 4 hemolytic anemia event(s), the clinical research team will confer with the Sponsor, Gilead, and Genentech to discuss the full safety profile including SAEs and DLTs. Minutes and formal decisions will be documented. Gilead and Genentech will be informed when decision is made to dose de-escalate due to observed DLTs. Decisions about trial continuation will be made based on the efficacy data from prior patients at appropriate time points per the statistical plan.

All data will be collected in a timely manner and reviewed by the principal investigator or a lead associate investigator. Events meeting requirements for expedited reporting described in Section **7.2.1** will be submitted within the appropriate timelines.

The principal investigator will review adverse event and response data on each patient to ensure safety and data accuracy. The principal investigator will personally conduct or supervise the investigation and provide appropriate delegation of responsibilities to other members of the research staff.

#### **7.4.2 Safety Monitoring Committee (SMC)**

This protocol will be periodically reviewed by an intramural Safety Monitoring Committee, comprising physicians, biostatisticians and a lay member selected based on experience, area of expertise, reputation for objectivity, absence of conflicts of interest and knowledge of or experience with clinical trial research. Initial review will occur as soon as possible after the annual NIH Intramural IRB continuing review date. Subsequently, each protocol will be reviewed as close to annually as the quarterly meeting schedule permits or more frequently as may be required by the SMC based on the risks presented in the study. For initial and subsequent reviews, protocols will not be reviewed if there is no accrual within the review period. The SMC will operate under the rules of an approved charter that will be written and reviewed at the organization meeting of the SMC. Each review will focus on unexpected protocol-specific safety issues that are identified during the conduct of the clinical trial.

Written outcome letters will be generated in response to the monitoring activities and submitted to the Principal investigator and Clinical Director or Deputy Clinical Director, CCR, NCI.

